8.5.1 Exploratory Assessments (B & T Lymphocyte Subsets) Analysis

As part of an exploratory analysis, blood samples will also be collected for quantification of B and T lymphocyte subsets to assess the effect of treatment on lymphocyte subpopulations. The results of these assessments will be presented in tabular form, and the outcome of the exploratory analyses of these results may be reported separately.

8.6 Vital Signs

Vital signs will be assessed at baseline and throughout the study. Vital signs will be summarized by study visit and will include descriptive statistics such as mean, median, standard deviation, minimum, and maximum for the value of the parameters and the changes from baseline.

8.7 Immunogenicity

Serum samples for antibodies to mapatumumab will be obtained at baseline (prior to dosing on Cycle 1/Day 1), prior to dosing on Day 1 of Cycles 1, 2, 4, 6, every 2 cycles thereafter, and at the End of Treatment visit (at least 30 days after the last dose). Rates of antibody response (persistent positive, transient positive, and negative) will be tabulated, and all data will be summarized in listings. A persistent positive immune response is defined as a subject who has 2 or more positive samples or for whom the last sample is positive. A transient positive response is defined as a subject who has only 1 positive response (if it is not the last sample). In these definitions, all data are counted, including baseline.

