1.6 Rationale for Dose Selection

As of June 2010, mapatumumab has been administered with chemotherapy (ie, carboplatin/paclitaxel, gemcitabine/cisplatin, bortezomib, or sorafenib) to 234 subjects, including 61 subjects who received 20 mg/kg and 50 subjects who received 30 mg/kg mapatumumab. Based on available data, mapatumumab in combination with chemotherapy is generally well tolerated at dose levels up to and including 30 mg/kg, and no significant safety issues have been observed in the course of the clinical trials even at the higher doses.

Preliminary PK data are available for subjects who received 1, 10, 20 or 30 mg/kg mapatumumab in combination with gemcitabine and cisplatin (n = 49), 10 or 30 mg/kg mapatumumab in combination with paclitaxel and carboplatin (n = 73), and 3, 10, or 30 mg/kg mapatumumab in combination with sorafenib (n = 17). Serum or plasma mapatumumab concentrations are consistently within the range of expected concentrations predicted from Phase 1 study results in solid tumor patients administered mapatumumab as monotherapy. Mapatumumab PK is linear and not affected by the addition of therapeutic agents. As expected, the observed peak and trough levels of mapatumumab at 30 mg/kg are 2 to 3 times higher than those observed at 10 mg/kg. Exposure appears to increase in proportion to dose and exposures for a given dose are similar across studies.

A Phase 1b dose escalation study of mapatumumab in combination with sorafenib in subjects with advanced hepatocellular carcinoma who are positive for hepatitis B surface antigen or hepatitis C antibody is being conducted. Safety observations have been consistent with the underlying disease and known sorafenib toxicities. As of June 2010, 6 subjects have received 3 mg/kg, 9 subjects have received 10 mg/kg, and 1 subject has received 30 mg/kg mapatumumab. The number of cycles completed ranges from 1 to 20; 4/16 (25.0%) of subjects have completed 11 or more cycles. Adverse events have generally been consistent with published reports of the toxicities associated with sorafenib and previous experience with mapatumumab, as well as underlying disease. The most frequently occurring treatment-emergent adverse events, regardless of severity or attribution of causality,

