5.1.3 Mapatumumab/Placebo Dose, Route of Administration and Schedule

The dose of mapatumumab is 30 mg/kg. Mapatumumab dose calculations will be based upon the subject's weight measured on Day 1 or within 3 days before Day 1 of each cycle. The planned duration of each treatment cycle will be 21 days. Mapatumumab/placebo will be administered on Day 1 of each cycle.

After reconstitution with sterile water for injection, the calculated mapatumumab dose to be administered to the subject will be further diluted in normal saline to a total volume of 250 mL for intravenous infusion. After adding the reconstituted product, the bag will be gently inverted to mix the solution. Following reconstitution and/or dilution in normal saline, mapatumumab will be stored at 2-8°C. The product will be administered to the subject within 8 hours of reconstitution. Refer to the HGS1012-C1103 Pharmacy Manual for instructions on admixing and administering study agent.

Two hundred-fifty mL normal saline solution for intravenous infusion will be administered as placebo for mapatumumab.

Mapatumumab/placebo will be infused at a constant rate over 1 hour.

Infusion and hypersensitivity reactions may occur. A suggested pre-medication regimen for mapatumumab/placebo consists of diphenhydramine and acetaminophen administered within 1 hour prior to the start of the mapatumumab/placebo dose. Use of a pre-medication regimen and alternatives to this regimen are at the investigator's discretion.

Subjects will be monitored closely during and after infusion for any sign of acute adverse reaction. If an allergic reaction occurs, see Section [5.1.5](#) and [Appendix 8](#) for suggested medical management.

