- ⁴ Immunogenicity: Obtain prior to dosing on Day 1 of Cycles 1, 2, 4, 6, every 2 cycles thereafter and at the end of treatment visit (at least 30 days after the last dose). On days when immunogenicity and pharmacokinetic samples are collected they will be collected together.
- ⁵ Pharmacokinetics: Blood specimens will be collected for determination of serum mapatumumab concentrations from subjects as follows: Cycle 1 (on Day 1 prior to the administration mapatumumab/placebo and at the completion of the mapatumumab/placebo infusion, and on Day 8), Cycles 2, 4 and 6 and thereafter on each even cycle (prior to dosing on Day 1, on the day of each disease assessment, and at the end of treatment visit (at least 30 days after the last dose). On days when immunogenicity and pharmacokinetic samples are collected they will be collected together.
- ⁶ Biomarkers: For subjects participating in the optional biomarker sub-study, historical biopsy samples will be collected, if available, and samples will be collected if obtained during the treatment period in Cycle 1 Days 1 (pre-dose mapatumumab), 2, 3, 8 and 15 and Cycle 2 Days 1 (pre-dose mapatumumab), 3, 8 and 15. In addition, blood samples will be obtained as follows: blood for isolation of DNA will be collected once, preferably in Cycle 1. Blood for isolation of serum will be collected in Cycles 1 and 2 (pre-dose on the day of mapatumumab/placebo dosing). Further details on the biomarker sub-study are outlined in [Appendix 6](#).
- ⁷ Study Agent Administration: Sorafenib will be administered at a dose of 400 mg twice daily without food (at least 1 hour before or 2 hours after a meal). On days when both sorafenib and mapatumumab/placebo are administered together, sorafenib should be taken at the same time as any other calendar day.
- ⁸ Vital Signs: Blood pressure will be monitored weekly for the first 6 weeks. Vital signs will be obtained within 30 minutes prior to administration of mapatumumab/placebo and at the end of infusion on Day 1 of each cycle. For subjects in the Extended Access Phase, only BP is required to be monitored and this should be performed every 6 weeks (\pm 3 days).
- ⁹ Body Weight: To be obtained on the day of or within 3 days before dosing on Day 1 of each cycle.
- ¹⁰ Performance Status: Obtained prior to dosing on Day 1 of each cycle.

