6.3 Completion Status

Subjects will continue to receive study agent(s) until radiologic disease progression or unacceptable toxicity. Subjects unable to tolerate sorafenib may continue to receive mapatumumab/placebo every 21 days until radiologic disease progression. Subjects unable to tolerate mapatumumab/placebo may continue to receive sorafenib until radiologic disease progression. All subjects will have an End of Treatment visit at least 30 days after the last dose of sorafenib and/or mapatumumab/placebo, whichever is later. After discontinuation of treatment, subjects will continue to be followed for radiologic disease assessments every 6 weeks, starting 6 weeks after the previous disease assessment while on treatment, until documented radiologic disease progression (if not previously documented) and then every 3 months thereafter for survival until at least 90% of the subjects have met the survival endpoint. After discontinuation of study treatment, all subjects will return 1 day after cycle completion (approximately Day 22) and at least 30 days after the last dose of sorafenib and/or mapatumumab/placebo.

Completion will be summarized with respect to completion of the planned course of treatment, completion of required short-term follow-up and completion of required long-term follow-up. Completion of the planned course of treatment will be satisfied by subjects who are treated until radiologic disease progression. Completion of short-term follow-up will be satisfied by subjects who are followed through at least 30 days after the final dose (of any study agent) for scheduled safety assessments (or a pending disease assessment visit to confirm disease response if required), regardless of the reason for treatment discontinuation. Completion of long-term follow-up will be satisfied by those subjects who are followed for overall survival (OS). Completion of the study is defined as completing study treatment, completing short-term follow-up and completing long-term follow-up. Subjects still being followed at the time of any analysis will be counted as "ongoing".

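### SAP 8.7 does not use the paired drug concentration to qualify antibody results in the mapatumumab arm, so the antibody rate could be understated if the assay does not tolerate drug at sampling levels

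*SAP*

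**What the plan says.** The dose and schedule are in Protocol 5.1.3: "The dose of mapatumumab is 30 mg/kg" and "The planned duration of each treatment cycle will be 21 days". Antibody samples follow footnote 4 of Table 6-1 (Protocol 6.3): "Obtain prior to dosing on Day 1 of Cycles 1, 2, 4, 6, every 2 cycles thereafter and at the end of treatment visit". SAP 8.7 repeats that schedule. SAP 6.3 times the final visit: "All subjects will have an End of Treatment visit at least 30 days after the last dose of sorafenib and/or mapatumumab/placebo, whichever is later".

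SAP 8.7 then states the output: "Rates of antibody response (persistent positive, transient positive, and negative) will be tabulated, and all data will be summarized in listings". A subject is persistent positive with two or more positive samples or a positive last sample, and transient positive with a single positive that is not the last. Negative is not defined. Every sample counts towards these definitions, baseline included, so none is set aside because drug was present.

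The drug level at the same moment is available. Footnotes 4 and 5 of Table 6-1 place a pharmacokinetic sample at each antibody time point and add: "On days when immunogenicity and pharmacokinetic samples are collected they will be collected together". SAP 8.7 does not refer to these concentrations. SAP 9 uses them for pooled population modelling and for graphic and tabular summaries.

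**The concern.** Circulating drug can bind anti-drug antibody and hide it from an assay with limited drug tolerance. Above that limit, an undetected result cannot separate absence of antibody from antibody bound to drug. On treatment, every scheduled post-dose sample in the mapatumumab arm is a trough under repeated dosing, so drug is expected to be present to some degree.

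With no inconclusive class, a mapatumumab-arm subject with no positive sample can only be tabulated as negative, whatever the drug level. Likewise, a subject with an early positive followed by samples in which antibody is hidden is tabulated as transient, although nothing shows that the response ended.

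Antibody response is a listed safety variable (SAP 8.1, Protocol 9.4.1). Protocol 5.1.5 records two allergic-type serious adverse events already considered related to mapatumumab. A low reported rate would naturally be read as reassurance. As the plan stands, the table could not tell that apart from assay interference.

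**Working it through.** The plan states no figure to reproduce here. On drug level it gives only a ratio, in Protocol 1.6: "the observed peak and trough levels of mapatumumab at 30 mg/kg are 2 to 3 times higher than those observed at 10 mg/kg". It gives no absolute concentration, half-life or volume. The only assay it names, an ELISA, measures drug (SAP 9, Protocol 9.5.2); the antibody assay and its drug tolerance are not described.

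**Inputs from the documents:** dose 30 mg/kg; interval 21 days; antibody samples before Cycles 2, 4, 6 and every second cycle after, then at End of Treatment; linear pharmacokinetics (Protocol 1.6), which permits adding doses.

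**Assumed inputs, not in the documents:** distribution volume V of 40-100 mL/kg; half-life h of 7-28 days; one compartment, bolus dosing.

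**Formula:** with n doses given and t days since the last, C = (30/V) × 1000 × Σ 2^(−(t+21i)/h), for i = 0 to n−1, in µg/mL. The initial level after one dose is 30/100 × 1000 = 300 at V = 100, and 30/40 × 1000 = 750 at V = 40.

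| Sample (µg/mL) | Lowest (V 100, h 7) | Highest (V 40, h 28) |
|---|---|---|
| Before Cycle 2 (1 dose, 21 days) | 300 × 2^(−3) = 37.5 | 750 × 2^(−0.75) = 446 |
| Before Cycle 4 (3 doses) | 42.8 | 869 |
| Before Cycle 6 (5 doses) | 42.9 | 1018 |
| 30 days after a single dose | 300 × 2^(−30/7) = 15.4 | 750 × 2^(−30/28) = 357 |
| 30 days after the fifth dose | 17.6 | 815 |

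**Sensitivity to half-life.** At 5 days the level before Cycle 2 is 16-41 and at 30 days after the last dose about 5-12. At 3 days these are 2.3-5.9 and below 1.

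**Sensitivity to assay tolerance.** At an illustrative limit of 10 µg/mL, every level in the table exceeds it. At 100 µg/mL the result is mixed: before Cycle 2, for example, V = 40 with h = 7 gives 94, while V = 100 with h = 14 gives 106. A limit above the levels actually reached would leave nothing masked.

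**Unaffected samples.** Placebo is normal saline (Protocol 5.1.3), so drug is zero throughout that arm, about half the subjects. In the mapatumumab arm the final visit follows the later of the two agents' last doses, and sorafenib may continue after mapatumumab stops (SAP 6.3). If mapatumumab stops after two doses, the level is 0.05-129 at 90 days, 0-14 at 180 days and 0-3 at 240 days. After six doses it falls below 10 µg/mL at 36-209 days and below 1 µg/mL at 59-302 days.

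**Transient class.** Troughs rise from Cycle 2 to Cycle 6 by a factor of 42.9/37.5 = 1.14 at one end of the range and 1018/446 = 2.28 at the other. An antibody detected before Cycle 2 could therefore be hidden later, and the subject labelled transient. Masking can also hide a subject's only positive sample, which moves that subject from transient to negative.

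**The case against.** The strongest reply is that this is a descriptive safety summary. Antibody response is not among the study endpoints in the protocol synopsis, it is not tested, and it drives no decision. Antibody results go into listings and concentrations are presented in the study report, so a careful reader could qualify the negatives without any change. That limits the importance of the point. It does not repair the tabulated rate, which is what most readers will see.

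Second, masking is not demonstrated. This stands: everything depends on an assay tolerance that the documents do not give. Protocol 1.4.2 reports one antibody-positive monkey of 40, in the 50 mg/kg group, but not whether drug was present in that sample, so it settles nothing either way.

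Third, a reader might infer that every sample after the first dose is uninterpretable when negative. The documents do not support that, because placebo subjects carry no drug and some End of Treatment samples can be essentially drug-free.

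A reader might also take SAP 8.7 to direct that each undetected sample be counted as negative. It does not. It classifies subjects, and negative is an undefined residual class.

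**Conclusion.** The point holds in conditional form. SAP 8.7 neither defines negative nor provides an inconclusive class, and it leaves unused the paired concentration that would show which mapatumumab-arm results can be relied on. If the assay does not tolerate the drug levels at sampling, the antibody rate could be understated and some persistent responses could appear as transient or negative.

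Under the stated assumptions (V 40-100 mL/kg, half-life 7-28 days), those levels are about 38-1000 µg/mL before Cycles 2 to 6 and about 15-815 µg/mL exactly 30 days after the last mapatumumab dose. No size can be put on the error in the rate itself without the assay's tolerance.

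Two stronger conclusions should not be drawn. One is that the rate is biased towards zero as a matter of fact; with a tolerant assay there is no such bias. The other is that the share of transient responses is inflated; masking moves subjects both into and out of that class, and the net direction is not established. The change is still worth making, because it improves a listed safety variable using data already collected.

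**What to change.** In SAP 8.7, state the antibody assay's drug-tolerance limit and, for the mapatumumab arm, give every subject one class:

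- *Persistent positive*: as now.
- *Transient positive*: a single non-final positive with a later conclusive negative, meaning an undetected sample whose paired concentration is below the limit.
- *Positive, persistence undetermined*: a single non-final positive without such a later sample.
- *Negative*: no positive sample, and at least the last post-dose sample has a paired concentration below the limit.
- *Inconclusive (drug present)*: no positive sample and the condition for negative not met.

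Report by arm, with the positive rate both among all subjects and among conclusive subjects, and show the number inconclusive. The second rate should be read with care: positives count as conclusive at any drug level and negatives do not, so it can overstate.

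The cost is SAP wording and a merge with concentrations drawn at the same visits. Fewer subjects can be called antibody negative, and the tolerance limit must be available, which the documents do not show. If the assay proves tolerant of the levels reached, the table will barely change and its negatives will be defensible.

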1.4.2 Non-Clinical Mapatumumab Safety Studies

To assess the nonclinical safety of mapatumumab, a 6-month toxicity study, with a 4-month recovery period, was conducted in chimpanzees. Mapatumumab was administered intravenously at up to 40 mg/kg every 10 days. No mapatumumab-specific toxicity was identified and no anti-mapatumumab antibodies were detected.

To assess its off-target effects, mapatumumab was administered intravenously weekly to cynomolgus monkeys, whose TRAIL R1 homolog does not bind mapatumumab. Mapatumumab was well tolerated at doses of up to 50 mg/kg and was not highly immunogenic: of the 40 monkeys treated, 1 developed anti-mapatumumab antibodies. The positive response was observed in an animal in the high dose (50 mg/kg) group.

In vitro, mapatumumab was found to decrease viability of normal human hepatocytes, although the observed effect was less than that observed with TRAIL. This effect was variable across donors and did not amplify with increasing concentrations of mapatumumab. It should

be noted that in clinical studies, plasma mapatumumab concentrations have been achieved that are > 1100-fold greater than the minimum exposure resulting in reduced in vitro hepatocyte viability. Despite this, the clinical results do not reveal evidence of hepatotoxicity in those studies. Hence it appears that the in vitro hepatocyte viability assay is not predictive of mapatumumab effects *in vivo*.

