4.2 Exclusion Criteria

Subjects will be excluded from participating in the study if they meet any of the following exclusion criteria:

1. Any co-morbid condition that in the judgment of the investigator renders the subject at high risk of treatment complications or reduces the possibility of assessing clinical effect.
2. Received prior investigational or non-investigational cytotoxic chemotherapy, hormonal therapy, biological therapy (including but not limited to monoclonal antibodies, small molecules or other immunotherapy) to treat hepatocellular carcinoma.
3. History of organ allograft.
4. Previously received mapatumumab or sorafenib.
5. Underwent resection, radiofrequency ablation, radiation or chemoembolization within 4 weeks before enrollment or not recovered from such treatments.
6. Need for concomitant anticancer therapy (surgery, radiation therapy, chemotherapy, immunotherapy, radiofrequency ablation) or other investigational agents during the study treatment period.
7. Major surgery (ie, the opening of a major body cavity, requiring the use of general anesthesia) within 4 weeks before enrollment; minor surgery (except for insertion of vascular access device) within 2 weeks before enrollment; or not yet recovered from the effects of the surgery.
8. Systemic steroids within 1 week before enrollment except steroids used as part of an antiemetic regimen or maintenance-dose steroids for non-cancerous disease.
9. Hepatic encephalopathy, per the investigator's evaluation.
10. History of clinically significant gastrointestinal bleeding requiring procedural intervention (eg, variceal banding, transjugular intrahepatic portosystemic shunt procedure, arterial embolization, topical coagulation therapy) within 4 weeks before enrollment.
11. Gastrointestinal disease resulting in an inability to take oral medication or a requirement for intravenous hyperalimentation.
12. History of any infection requiring hospitalization or intravenous antibiotics within 2 weeks before enrollment.
13. Known brain or spinal cord metastases unless adequately treated (surgery or radiotherapy) with no evidence of progression and neurologically stable off anticonvulsants and steroids.
14. Known human immunodeficiency virus infection.

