4.1 Choice of Control Group

The control group in this study is Arm A: sorafenib 400 mg orally twice daily continuously in each cycle + placebo intravenously on Day 1 of each cycle. The control group will be used for comparison purposes for both primary and secondary efficacy and safety analyses. It will also be used to provide a measure of internal validity to the interpretation of results from the sorafenib + mapatumumab 30 mg/kg study arm, commensurate with consistency of observed outcomes in the sorafenib + placebo study arm to historical outcomes in this patient population.

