4.6 Interim Analysis

This study has no interim analysis planned.

5 General Statistical Considerations

Statistical analyses performed on the efficacy data will be applied to a modified intention-to-treat (MITT) population unless stated otherwise. This population is defined as the set of all randomized subjects who receive at least part of 1 dose of study agent (mapatumumab/placebo and/or sorafenib) with subjects analyzed according to the groups to which they are randomized, regardless of the treatment they subsequently receive. Additional analyses may be performed on the as-treated population, defined as the set of subjects receiving at least part of 1 dose of study agent analyzed according to the treatment that they actually receive. All analyses performed on safety, subject disposition, exposure and completion status will be applied to the as-treated population. Analyses performed on demographics and concomitant medications data will be applied to the MITT population.

Assessments will be referred to by day of cycle beginning with Cycle 1/Day 1. This will allow data from subjects with small fluctuations in cycle length, or dosing delays to be reported in a consistent fashion. Cycle 1/Day 1 (predose) will typically be the baseline assessment unless data are missing, in which case screening data closest to the Cycle 1/Day 1 assessment will be used. In the instance a subject discontinues all treatment, or discontinues mapatumumab/placebo, but remains on sorafenib treatment, an off-treatment distinction will be made when referencing disease assessments.

Categorical data analyses using the Pearson chi-square test will substitute Fisher's exact test if > 20% of expected contingency table cell counts are < 5.

Analyses will be performed using the SAS SystemTM, WinNonlin Enterprise EditionTM, StatXactTM, and the R statistical package.

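### SAP 8.7 counts the pre-dose sample in its antibody-response classes and does not split by baseline status, so the table mixes reactivity present before mapatumumab with antibody formed after it

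*SAP*

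**What the plan says.** SAP 8.7 plans to tabulate rates of antibody response in three classes and to put all data in listings. For the persistent class the wording is: "A persistent positive immune response is defined as a subject who has 2 or more positive samples or for whom the last sample is positive". The transient class covers a single positive result that is followed by at least one later sample. The section then closes with "In these definitions, all data are counted, including baseline".

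On timing, footnote 4 to Table 6-1 (Protocol 6.3) says: "Obtain prior to dosing on Day 1 of Cycles 1, 2, 4, 6, every 2 cycles thereafter and at the end of treatment visit". SAP Section 5 agrees that "Cycle 1/Day 1 (predose) will typically be the baseline assessment". Protocol 4.2 excludes anyone who "Previously received mapatumumab or sorafenib". Anti-mapatumumab antibody response is a named safety variable in Protocol 9.4.1 and SAP 8.1. The protocol does not define the classes, and neither document defines a treatment-emergent antibody category.

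**The concern.** A reader will take a rate of antibody response to mapatumumab as the rate of antibody formed after exposure. In an eligible subject, reactivity in the pre-dose sample must have some other source, yet the rule counts it toward a response. Two features combine: the baseline sample is counted in the classes, and results are not separated by baseline status.

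The SAP handles its other safety data differently. Adverse events are summarised as treatment-emergent (8.2), laboratory tables show shifts from baseline (8.5), and vital signs include changes from baseline (8.6). For antibodies, baseline is pooled into the outcome. At stake is the reading of one safety table for a recombinant protein for which Protocol 5.1.5 already reports two related allergic serious adverse events.

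**Working it through.** **Step 1. Apply the class rules literally.** Take a baseline sample and three later samples, and compare the label under SAP 8.7 with the label from post-dose samples only.

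| Baseline | Later samples | SAP 8.7 | Post-dose only |
|---|---|---|---|
| + | − − − | transient | negative |
| + | + − − or − + − | persistent | transient |
| + | − − +, + + −, + − +, − + +, + + + | persistent | persistent |
| + | none taken | persistent (baseline is the last sample) | not evaluable |
| − | any of the 8 patterns | unchanged | unchanged |

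Counting baseline changes 3 of the 8 baseline-positive patterns. In the other 5 the subject is persistent either way. The table enumerates the rule; the patterns are not frequencies.

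**Step 2. Direction.** Among subjects with at least one post-dose sample, counting baseline can only raise the any-positive and persistent rates. The transient rate can move either way: the first row enters that class and the second row leaves it.

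**Step 3. Size.** The plan gives no antibody rate to reproduce, so every input here is an assumption:

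- b: proportion positive at baseline.
- e: proportion of baseline-negative subjects who become positive after dosing.
- q: chance that all later samples are negative, given a positive baseline.
- Every subject has at least one post-dose sample.

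Tabulated any-positive rate: t = b + (1−b)e.

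Excess over the incidence among baseline-negative subjects: t − e = b(1−e).

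| e | b = 0 | 1% | 2% | 5% | 10% |
|---|---|---|---|---|---|
| 2.5% | 2.50 | 3.48 | 4.45 | 7.38 | 12.25 |
| 5% | 5.00 | 5.95 | 6.90 | 9.75 | 14.50 |
| 10% | 10.0 | 10.9 | 11.8 | 14.5 | 19.0 |

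(t in %. The 2.5% row borrows its scale from Protocol 1.4.2, where "of the 40 monkeys treated, 1 developed anti-mapatumumab antibodies"; it is not a human figure and says nothing about b.)

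**Step 4. The part due to counting baseline alone.** With post-dose samples only and all subjects kept, the rate is r = b(1−q) + (1−b)e, so t − r = bq. At b = e = 5%, t = 0.05 + 0.95 × 0.05 = 9.75%, which is 4.75 points above e.

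- q = 0: t − r = 0 and r = 9.75%. Deleting the sentence changes nothing.
- q = 0.5: t − r = 2.5 points and r = 7.25%.
- q = 1: t − r = 5 points and r = 4.75%, just under e because baseline-positive subjects stay in the denominator.

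**Step 5. Would it arise?** The chance of at least one baseline-positive subject among 50 is 1 − (1−b)^50: 39.5%, 63.6%, 92.3% and 99.5% at b = 1, 2, 5 and 10%.

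**Step 6. One sample or two?** SAP 8.7 names the pre-dose Cycle 1/Day 1 draw twice, once as baseline and once in the cycle list. The protocol footnote lists it once. If it were counted twice, a single baseline positive would become persistent.

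**The case against.** The strongest reply is that the placebo arm shows the background. SAP 8.7 does not say the table is by arm, but SAP 4.1 states: "The control group will be used for comparison purposes for both primary and secondary efficacy and safety analyses". SAP Section 5 and 8.1 also put safety on the as-treated population, so by-arm presentation is the natural reading. If b is equal in both arms and no antibody emerges on placebo, the arm difference in any-positive rates has expectation (1−b)e.

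That stands as partial mitigation. It corrects neither arm's rate nor any subject's label, and it is noisy. The chance difference in baseline positives between two arms of 50 has SD √(2 × 50 × b(1−b)) = 1.0, 1.4, 2.2 and 3.0 subjects at b = 1, 2, 5 and 10%. The expected emergent count, 50(1−b)e at e = 5%, is only 2.48, 2.45, 2.38 and 2.25.

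Three further replies are fair. The listings keep every result, so baseline-positive subjects can be found. The rule is prespecified and cannot hide a positive sample. No hypothesis test or efficacy endpoint uses the table. These limit the weight of the point but do not make the labels right.

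A reader might also infer that the quoted sentence causes all the mixing, so that deleting it would be enough. Steps 1 and 4 show otherwise: subjects who remain positive after dosing are tabulated as responders with or without it.

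**Conclusion.** The point holds as a defect in a descriptive safety table and should be corrected. As written, SAP 8.7 labels some pre-dose reactivity as antibody response, and the missing split by baseline status leaves the rest mixed in.

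The any-positive rate exceeds the incidence among baseline-negative subjects by b(1−e). Counting baseline itself contributes bq, anywhere from 0 to b. Both b and e are assumptions, and the effect is zero if no subject is baseline-positive.

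Two stronger readings are not supported. It might be inferred that every tabulated rate is overstated, but the transient rate can fall. It might be inferred that baseline reactivity is material in this trial, but neither document gives a human antibody rate or an assay false-positive rate. The time-to-progression analysis is untouched.

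**What to change.** Replace the last sentence of SAP 8.7 with:

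> Persistent positive, transient positive and negative are assigned from post-dose samples only, and are tabulated by treatment arm and by baseline status (positive, negative) with denominators. The rate of treatment-emergent antibody is reported among baseline-negative subjects with at least one post-dose sample. Subjects with no post-dose sample are not evaluable. The baseline sample and the pre-dose Cycle 1/Day 1 sample are one sample.

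Cross-tabulating is better than removing baseline-positive subjects from the classes, because it keeps the persistent/transient distinction for them.

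The cost is a few sentences and some extra table cells; the samples are already scheduled. The limit is that, without titre data, a boosted response in a baseline-positive subject cannot be identified. The present rule cannot identify one either.
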